5.2.2.3. Disease-Related Emergency Room Visits and In-Patient Hospitalizations

Change from baseline in the total number of disease-related emergency room visits and in-patient hospitalizations per 28 days in double-blind period will be summarized descriptively. In addition, the number of subjects with disease-related emergency room visits and in-patient hospitalizations and the number of disease-related emergency room visits and in-patient hospitalizations, will be tabulated by frequency and percent for double-blind period for ITT population.

- Age group (<8 years old vs ≥ 8 years old)

A similar analysis will be performed for change from baseline in the total number of disease-related emergency room visits and in-patient hospitalizations per 28 days during the double-blind period for ITT population. This analysis will exclude subjects that have a DNR order or had COVID-19 during the double-blind period.

5.2.2.4. Rescue Medications for Seizures

Number of rescue medication uses and the number of subjects taking rescue medications will be summarized descriptively and tabulated by frequency and percent separately for double-blind period for ITT population. In addition, number of rescue medication uses and the number of subjects taking rescue medications will be tabulated by frequency and percent for double-blind period for ITT population.

- Age group (<8 years old vs ≥ 8 years old)

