2.2.2. Secondary Endpoints

Key secondary efficacy endpoints of the study are as follows:

- Number of disease-related hospitalization days
- Occurrence or recurrence of status epilepticus

Other Secondary endpoints are as follows:

- Number and percent of subjects with disease-related in-patient hospitalization/emergency room visits
- Number of disease-related in-patient hospitalization admissions/emergency room visits
- Percent change from baseline in total seizure frequency per 28 days of all types
- Proportion of subjects with $\geq 25\%$, $\geq 50\%$, $\geq 75\%$, and 100% reduction in motor seizures
- Proportion of subjects with $\geq 25\%$, $\geq 50\%$, $\geq 75\%$, and 100% reduction in total seizures
- Number of rescue seizure medications
- Health-related quality of life as measured by the CarerQoL-7D questionnaire
- Number of seizure clusters as defined by “too many to count” entries in the seizure diaries

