5.5. Concomitant Therapy

Any medication taken by a subject 30 days prior to Baseline Visit and during the course of the study and the reason for use of the medication will be recorded on the electronic case report form (eCRF)/paper case report form (CRF). During Screening, each subject will be instructed to report the use of any medication to the investigator. Subjects will also be instructed about the importance of not taking any medication throughout the study (including over-the-counter medications) without consulting the investigator.

All immunizations will be considered as concomitant medications and will be recorded in the CRF. Subjects will be instructed to consult the investigator before immunization. The final decision on any immunization should be made by the treating physician in consultation with the patient and/or caregiver.

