7.1.8. Rescue Medication Administration for Epilepsy

Use of rescue medications for epilepsy will be collected throughout the study and analyzed as a secondary study endpoint. The following standardized criteria should be used for use of rescue medications:

- Seizure lasting longer than 4 minutes
- Occurrence of status epilepticus
- Cluster of 15 or more seizures

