8.4.3. Analysis of Secondary Efficacy Endpoints

Change from baseline in number of disease-related hospitalization days per 28 days and change from baseline in occurrence/recurrence of status epilepticus per 28 days are the two key secondary endpoints. The treatment groups will be compared using Wilcoxon Rank-Sum Test. Number of disease-related hospitalization days and number of occurrence/recurrence of status epilepticus will be tabulated by frequency and percent as well.

Percent change from baseline in total seizure frequency per 28 days will be analyzed in a similar way to the primary endpoint.

Response rates (25%, 50%, 75%, and 100%) for motor seizure and total seizure will be tabulated by treatment groups and treatment will be compared by Cochran-Mantel-Haenszel test adjusting for stratifying factor.

Number of disease-related emergency room visits and in-patient hospitalizations, number of rescue seizure medications, and seizure clusters will be tabulated by frequency and percent. In addition, change from baseline in disease-related emergency room visits and in-patient hospitalizations per 28 days, and change from baseline in seizure clusters per 28 days will be summarized.

Health-related quality of life, as measured by the CarerQoL-7D questionnaire, will be summarized descriptively.

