5.2.1.1. Number of Disease-Related Hospitalization Days

Number of disease-related hospitalization days per 28 days will be calculated as the total number of disease-related hospitalization days multiplied by 28 and divided by the total number of days in the interval.

Disease related hospitalization is defined as any hospitalizations occurring as the consequence of an AE or SAE during the study period that is related to the subject's disease state or baseline conditions of the subject and lack of alternative explanation for the event. All the hospitalization events will be reviewed, classified as disease-related or not and agreed upon prior to the study unblinding.

The change from baseline in number of disease-related hospitalization days per 28 days during the double-blind period will be compared between the treatment groups using Wilcoxon rank-sum test for ITT population.

The number and the change from baseline in number of disease-related hospitalization days per 28 days during the double-blind period will be summarized descriptively for ITT population. Number of disease-related hospitalization days will be tabulated by frequency and percent as well for double-blind period, respectively, for ITT.

In addition, the change from baseline in number of disease-related hospitalization days per 28 days will also be summarized descriptively for the following subgroups for double-blind period for ITT population.

- Age group (<8 years old vs ≥ 8 years old)
- Sex (Male vs Female)
- Race (White vs Other)
- Region (United States vs Rest of the World)

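### Rescue-medication use is summarised only as raw uses and users over the double-blind period; a rate per 28 days of follow-up should be added, as for the comparable event endpoints

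*SAP*

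**What the plan says.** Protocol 2.2.2 lists the endpoint among the other secondary endpoints as "Number of rescue seizure medications". Protocol 7.1.8 adds: "Use of rescue medications for epilepsy will be collected throughout the study and analyzed as a secondary study endpoint".

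The planned summary is short. SAP 5.2.2.4 states: "Number of rescue medication uses and the number of subjects taking rescue medications will be summarized descriptively and tabulated by frequency and percent", for the double-blind period in the ITT population, with a breakdown by age group. Protocol 8.4.3 says only that "number of rescue seizure medications, and seizure clusters will be tabulated by frequency and percent". Neither gives a rate or a follow-up denominator. SAP 3.5, which defines run-in baselines for seizure frequency, hospitalization days and status epilepticus, does not mention rescue use.

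The comparable event endpoints are treated differently:

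- Hospitalization days (SAP 5.2.1.1) are "multiplied by 28 and divided by the total number of days in the interval". Status epilepticus (SAP 5.2.1.2) follows the same rule.
- SAP 5.2.2.3 plans "Change from baseline in the total number of disease-related emergency room visits and in-patient hospitalizations per 28 days in double-blind period".
- Motor seizure clusters (SAP 5.2.2.5) also get a change from baseline per 28 days.

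Under SAP 2.2.1 the double-blind period runs to the last study visit for subjects who do not continue into the extension. SAP 3.1.1 names withdrawal, noncompliance and death as intercurrent events. SAP 3.7 imputes nothing in general.

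**The concern.** A count of events accrues with time at risk. A subject who leaves at day 56 has one third of a completer's opportunity to record rescue use, and nothing in SAP 5.2.2.4 corrects for that. If the arms lose subjects at different rates or times, the mean number of uses and the percentage of users differ for a reason unrelated to treatment.

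The plan already deals with this for the neighbouring endpoints and, in SAP 6.2.3, for adverse events. It gives no reason for leaving rescue use out. Protocol 8.4.3 tabulates emergency room visits and admissions, rescue use and clusters in one sentence, then adds a per-28-day change for the other two only.

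What is at stake is the stated secondary objective on rescue medication (Protocol 2.1.2, SAP 1.2.2). The display also gives context for the primary result: SAP Table 1 handles rescue use by treatment policy, and SAP 3.1.1 plans no sensitivity analysis for it.

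**Working it through.** The documents give no rescue rate and no expected dropout, so there is no planned figure to reproduce. The inputs are:

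- Planned double-blind follow-up: 168 days, or six 28-day units (SAP 5.1.1).
- Assumed: the same true rescue rate in both arms, constant over time.
- Assumed: a share *d* of one arm stops after a fraction *f* of the 168 days, and nobody stops in the other arm.

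**Mean raw count.** Relative to the arm without stops, the ratio is (1 − *d*) + *d* × *f* = 1 − *d*(1 − *f*). The rate cancels.

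| *d* | *f* = 1/2 (day 84) | *f* = 1/3 (day 56) |
|---|---|---|
| 10% | 0.95 | 0.93 |
| 20% | 0.90 | 0.87 |
| 30% | 0.85 | 0.80 |

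For example, at one use per 28 days a completer has 6 uses and a day-56 stopper has 2. With *d* = 20% the arm mean is 0.8 × 6 + 0.2 × 2 = 5.2, and 5.2/6 = 0.87.

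**After dividing by follow-up.** In the same example mean follow-up is 0.8 × 6 + 0.2 × 2 = 5.2 units, so uses per 28 days are 5.2/5.2 = 1.00, equal to the other arm's 6/6. The ratio is 1.00 in every cell of the table.

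**Percentage of users.** At an assumed 0.25 uses per 28 days (Poisson), a completer has some use with probability 1 − exp(−1.5) = 77.7%, and a day-84 stopper with probability 1 − exp(−0.75) = 52.8%. With *d* = 20% the arm figure is 0.8 × 77.7 + 0.2 × 52.8 = 72.7%. At 1 use per 28 days or more, nearly every subject is a user and the effect is small.

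**If early stoppers use more rescue.** Let their rate be *k* times that of the others. The ratio of raw means becomes (1 − *d*) + *d* × *f* × *k*, which reaches 1 at *k* = 1/*f*: 2 times for a mid-period stop, 3 times for a day-56 stop. With *d* = 20%, *f* = 1/2 and *k* = 3 the ratio is 0.8 + 0.3 = 1.10, so the arm with more stops shows the higher count. The count still understates that arm's rate, which is 1.10 / (0.8 + 0.1) = 1.22 times the other arm's.

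**Change from run-in.** Suppose each subject has a stable Poisson rate, with mean *m* per 28 days and between-subject variance *s*². The double-blind rate over six units has variance *s*² + *m*/6. The change from a 28-day run-in has variance *m* + *m*/6. The change is more precise only if *s*² > *m*, that is, if the coefficient of variation exceeds 1/√*m*: 200% at *m* = 0.25, 100% at *m* = 1, 50% at *m* = 4.

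**The case against.** The strongest reply is that little depends on this endpoint. It is descriptive, carries no test and lies outside the fixed sequence in SAP 3.6, and the SAP implements the endpoint as the protocol words it. That stands, and it limits the weight of the point.

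The size also rests on one-sided dropout. One extra mid-period stop among 30 subjects moves the mean by only 1/30 × 0.5 = 1.7%. SAP 3.2 reports the median as well; if all subjects had the same rate, fewer than half stopping early would leave it unchanged. Unequal follow-up will be visible in the disposition table (SAP 4.1) and the exposure bands (SAP 6.1). All of this is fair, but showing follow-up elsewhere does not correct the count.

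Three stronger readings are tempting, and the documents do not support them:

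- **An arm with more deaths or early stops necessarily looks as if it needed less rescue.** That depends on the early stoppers' rescue rate, and above 1/*f* times the others' rate the direction reverses.
- **Wide variation in rescue use between subjects makes the objective impossible to judge at 30 per arm.** Under randomization such variation is sampling variance, not bias, and dividing by follow-up does not remove it.
- **A change from run-in is required and its data are already in hand.** Protocol 5.5 covers "Any medication taken by a subject 30 days prior to Baseline Visit and during the course of the study", but it records medications and reasons for use, not a number of uses. For the run-in, Protocol 7.1.1 names the seizure diary and hospital log, and Protocol 7.1.2 places explicit rescue tracking in the placebo-controlled phase. Protocol 7.1.8 makes run-in counts plausible without establishing them. The change score can also be the noisier measure.

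**Conclusion.** The point holds in limited form. Rescue use is the one event count among these endpoints with no follow-up denominator, and no other section supplies one. With equal true rates, the mean count in the arm with more early stops is about 5% to 20% lower. This assumes that 10% to 30% of that arm stop at one third to one half of 168 days and that nobody stops in the other arm. With balanced dropout the gap largely disappears; with much higher rescue use among early stoppers it shrinks or reverses; the median may be unaffected. The consequence is a possible misreading of a descriptive secondary endpoint. The primary conclusion and the type I error are untouched. This is an inexpensive improvement that follows the plan's own convention, not the repair of an error that changes a trial conclusion.

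**What to change.** In SAP 5.2.2.4, define rescue uses per 28 days as uses × 28 / days observed in the double-blind period of SAP 2.2.1, and summarise it by arm. State whether the day shared with the start of open-label treatment counts, and apply the same rule to numerator and denominator.

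Beside it, report total uses divided by total follow-up time in each arm. Individual rates from very short follow-up can be extreme: 4 uses in 7 days becomes 4 × 28/7 = 16 per 28 days. The pooled rate keeps such subjects from dominating. Show follow-up time by arm in the same table and keep the raw counts of uses and users.

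The sponsor should confirm whether individual uses were captured in the 28-day run-in. If so, show the run-in rate by arm descriptively as context. A change-from-baseline summary is optional, because it can add noise when rescue use is infrequent.

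The cost is a few lines of SAP text and one derived variable. The double-blind rate needs no new data; only the run-in display depends on what was recorded.

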5.2.2.5. Seizure Clusters

Motor Seizure cluster data are collected on diary. The number of subjects with motor seizure clusters, number of days with motor seizure clusters and change from baseline in total number of motor seizure clusters per 28 days will be summarized by frequency and percent for double-blind period for ITT population.

Change from baseline in total number of motor seizure clusters per 28 days will be summarized descriptively for double-blind period for ITT population.

- Age group (<8 years old vs ≥ 8 years old)

5.2.2.6. Quality of Life

Quality of life assessment includes CarerQoL-7D and visual analogue scale (VAS). The description of these two instruments and weighted sum derivation are from [Hoefman et al, 2013](#).

The CarerQoL-7D comprises five negative and two positive dimensions of lending informal care derived from a literature review of subjective burden measures. The five negative dimensions are (i) relational problems, (ii) mental health problems, (iii) problems combining daily activities with care, (iv) financial problems, and (v) physical health problems. The two positive dimensions are (i) fulfilment from caregiving and (ii) support with lending care. Respondents are asked to indicate whether an item applies to them with three possible responses: (i) no, (ii) some, and (iii) a lot of. The combination of items and answering categories yields 2187 ($= 3^7$) caregiving situations.

Answers on the negative dimensions of the CarerQoL-7D receive value of 0 (a lot), 1 (some) and 2 (no); answers on the positive dimensions receive a value of 0 (no), 1 (some), and 2 (a lot). Summing the values for the seven dimensions, a score of 0 thus translates to the worst informal care situation (a lot of problems and no support or fulfilment); the higher the score, the better the situation.

Recently, a tariff has become available for the CarerQoL ([Hoefman et al. 2013](#)), which enables researchers to calculate a weighted sum score of the CarerQoL-7D, taking the severity of problems into account ([Table 2](#)). The tariff is based on Dutch preferences for different caregiving situations and therefore concern Dutch national tariffs. Using the weighted sum score, the worst

caregiving situation receives a score of 0, while the best now has a score of 100. The scores between 0 and 100 can be calculated using the tariffs in [Table 3](#).

Table 3: National tariff CarerQoL-7D

Dimension	Tariff for score		
	no	some	a lot
Fulfilment	0	13.6	19.7
Relational problems	14.7	10.6	0
Mental health problems	13.3	9.3	0
Problems combining daily activities	10	6.4	0
Financial problems	14.3	10.6	0
Support	0	4.7	6.5
Physical health problems	15.1	15.1	0
Plus: a 'bonus' for:	no	yes	
No mental health problems and no physical health problems	0	6.6	

The CarerQoL-VAS, a valuation component, is a horizontal visual-analogue scale (VAS) measuring well-being of the informal caregiver in terms of general happiness, ranging from completely unhappy (=0) to completely happy (=10) (Brouwer et al. 2006).

The response to each of the CarerQoL dimensions will be summarized descriptively by visit for double-blind period for ITT population.

The weighted sum (based on the table above) of the answers will be derived for each subject. Change from baseline in the weighted sum and VAS will be summarized descriptively by visit for double-blind period respectively, for ITT population.

CarerQoL-VAS and the weighted sum data will be listed.

5.3. Tertiary/Exploratory Endpoint(s) Analysis

5.3.1. PedsQL

Child and Parent Reports of the PedsQL™ 3.0 Neuromuscular Module (<https://www.pedsq.org/score.html>) are composed of 25 items comprising 3 dimensions as shown in Table 4.

Table 4: Description of the Neuromuscular Module

Dimension	Number of Items	Cluster of Items	Reversed Scoring
About My Neuromuscular	17	1-17	1-17
Communication	3	1-3	1-3
About Our Family Resources	5	1-5	1-5

The scores are transformed on a scale from 0 to 100, higher scores indicate lower problems. The scoring procedure are:

- Step 1 transform Score. Items are reversed scored and linearly transformed to a 0-100 scale as follows: 0=100, 1=75, 2=50, 3=24, 4=0.
- Step 2: calculate scores by dimension.
 - If more than 50% of the items in the scale are missing, the scale scores will not be computed.
 - Mean score=sum of the items over the number of items answered.

Total score: sum of all the items over the number of items answered on all the scales. If more than 50% of the items in the scale are missing, the total score will not be computed.

Change from baseline in PedsQL score for each dimension and total score will be summarized descriptively by visit for double-blind period for ITT population.

PedsQL data and the score for each dimension along with the total score will be listed.

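### SAP 5.3.1 maps PedsQL response 3 to 24, but the linear rule it states gives 25

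*SAP*

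**What the plan says.** SAP 5.3.1 describes the PedsQL Neuromuscular Module as 25 items in three dimensions of 17, 3 and 5 items. The scale runs in the favourable direction: "The scores are transformed on a scale from 0 to 100, higher scores indicate lower problems". The item rule is: "Items are reversed scored and linearly transformed to a 0-100 scale as follows: 0=100, 1=75, 2=50, 3=24, 4=0". Dimension scores are averages: "Mean score=sum of the items over the number of items answered". The total is formed in the same way over all items, and a score is not computed when more than half its items are missing. The only planned use is descriptive: "Change from baseline in PedsQL score for each dimension and total score will be summarized descriptively by visit for double-blind period for ITT population". Protocol 2.2.3 and SAP 1.3.3 make PedsQL the exploratory endpoint.

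The query concerns SAP 5.2.2.6, which defines a weighted sum for the CarerQoL-7D from the tariffs in Table 3, plus a bonus of 6.6 when there are neither mental nor physical health problems. It gives the range: the worst "caregiving situation receives a score of 0, while the best now has a score of 100". This score is also summarised descriptively.

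**The concern.** The PedsQL map is an operative scoring instruction, and the only item-level one in the SAP. It calls itself linear and then prints five values that do not lie on a line. Anyone who programs the printed values will produce scores that are slightly wrong at one response level, the second worst. The error does not cancel from change scores unless the share of items answered 3 stays the same between visits. At stake is the correctness of the tabulated and listed PedsQL scores, not any hypothesis test.

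Two features of the CarerQoL-7D tariff invite a check for the same kind of slip: the best state does not sum exactly to the stated maximum, and one row repeats a value.

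**Working it through.** **PedsQL: inputs (SAP 5.3.1).** Responses x = 0, 1, 2, 3, 4; printed scores 100, 75, 50, 24, 0; dimension sizes 17, 3 and 5; total 25 items.

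**Step 1: the linear rule.** The line through (0, 100) and (4, 0) is score = 100 − 25x.

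| Response | Linear | Printed | Printed step |
|---|---|---|---|
| 0 | 100 | 100 | – |
| 1 | 75 | 75 | −25 |
| 2 | 50 | 50 | −25 |
| 3 | 100 − 25×3 = 25 | 24 | −26 |
| 4 | 0 | 0 | −24 |

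Four of the five values fit the line and only response 3 does not. An item moving from 2 to 3 loses 26 points and one moving from 3 to 4 loses 24, where each should lose 25.

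**Step 2: effect on a score.** Scores are means over answered items. With k items answered 3 out of n answered, the error is −k/n. For k = 1 and all items answered:

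- 17-item dimension: 1/17 = 0.06
- 3-item dimension: 1/3 = 0.33
- 5-item dimension: 1/5 = 0.20
- 25-item total: 1/25 = 0.04

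The maximum is n/n = 1.0, when every answered item is 3. Missing items raise the per-item figure, because n is the number answered, but not the ceiling. Under the SAP's missing-item rule the fewest answered items are 9, 2, 3 and 13, which give 1/9 = 0.11, 1/2 = 0.50, 1/3 = 0.33 and 1/13 = 0.08.

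**Step 3: effect on change from baseline.** The error in a change score is minus the change in the proportion of items answered 3. It is zero if that proportion does not move.

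**CarerQoL-7D: inputs (SAP Table 3).** Best-state tariffs are fulfilment 19.7, relational 14.7, mental health 13.3, daily activities 10, financial 14.3, support 6.5 and physical health 15.1; the bonus is 6.6.

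- *Stated range.* Scoring all 3^7 = 2187 response patterns gives a minimum of 0, as stated. The maximum is 19.7 + 14.7 + 13.3 + 10 + 14.3 + 6.5 + 15.1 + 6.6 = 100.2. One pattern exceeds 100; the next highest score is 98.4.
- *Rounding.* Eight terms printed to one decimal can each be off by 0.05, so the total can be off by 8 × 0.05 = 0.4 (0.35 if the printed 10 is exact). The 0.2 excess lies inside either bound. It is not a typical rounding result: with independent uniform rounding errors, the simulated total was off by 0.15 or more in 6.5% of draws and by 0.2 or more in 1.2%.
- *Physical health row.* 'No' and 'some' both carry 15.1. In the other problem rows the no-to-some step is 14.7 − 10.6 = 4.1, 13.3 − 9.3 = 4.0, 10 − 6.4 = 3.6 and 14.3 − 10.6 = 3.7. The bonus partly separates the two physical answers: with no mental health problems, moving from 'no' to 'some' costs 6.6; with any mental health problems it costs 0.

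**The case against.** On PedsQL, the fair reply is about size. The 1.0-point ceiling requires every answered item to be 3, and one such item among 25 moves the total by 0.04. The same map applies to both arms, the endpoint is exploratory, and no test uses it. The SAP also cites the instrument's scoring algorithm, so a programmer has something to check against. All of that stands and is why the point is minor. None of it makes 24 consistent with a linear map.

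On CarerQoL-7D, a reader might infer that this score is mis-scored too. The documents do not support that. A 0.2 excess is within what rounding can produce, and it affects a single response pattern. A reader might also infer that the physical health row was mis-copied and that its no-to-some step ought to resemble the 3.6 to 4.1 seen in the other rows. Nothing in the SAP requires the steps to be alike, and some of the value of having no physical problems sits in the separate bonus. Against that, the mental health row shares the bonus and still separates 'no' from 'some', so the bonus does not fully account for the repeated 15.1. The row therefore merits a look, but only the cited tariff can settle it.

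**Conclusion.** The PedsQL item rule is wrong as written: response 3 should be 25 under the SAP's own linear rule, and this needs no outside source. If coded literally, scores are low by the fraction of answered items equal to 3: 0.06, 0.33, 0.20 or 0.04 points per such item on complete questionnaires, and never more than 1.0. The documents do not show whether the program actually uses 24; the sizes assume that it follows the printed text. The point is minor. PedsQL is exploratory and descriptive, and it is absent from the fixed sequence in SAP 3.6, so no formal conclusion changes.

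For CarerQoL-7D the finding is a query only. The best state sums to 100.2, which is compatible with rounding, and the repeated 15.1 contradicts no statement in the SAP. No corrected tariff can be derived from the documents.

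**What to change.** Change 3=24 to 3=25 in SAP 5.3.1, and confirm that the scoring program returns 100, 75, 50, 25, 0 for responses 0 to 4.

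Separately, check SAP Table 3 cell by cell against the tariff it cites before programming, starting with the physical health row. If the table is a faithful copy, add a sentence saying so and stating how the 100.2 best state is reported. While there, correct the cross-reference in SAP 5.2.2.6 that first points to Table 2 for the tariff: Table 2 is the on-vatiquinone visit schedule.

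The cost is minutes: a one-character SAP correction, a program check and one look at the source. No data collection, test or sample size is affected.
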